## Safety analysis

The percentage of patients reporting the occurrence of treatment emergent adverse events classified by MedDRA System Organ Class (SOC) and Preferred Term (PT) will be presented by group with exact 95% Confidence Interval (CI) from study start to study end (Week-20 visit). No statistical test will be performed to compare incidences between groups due to the lack of power and issues with multiplicity testing.

The same table will be provided for adverse events of severe intensity and for adverse events related to study treatment.

The overall percentage of patients reporting at least one adverse event and at least one serious adverse event will also be computed with exact 95% CI.

All serious adverse events will be detailed in listings with start date, duration in days, intensity, causality assessment, action taken, outcome and dates of first and last study treatment administration.

The overall percentage of patients reporting injection site reactions will also be presented by group with exact 95% CI together with the evolution at 16 weeks since baseline of laboratory parameters (full blood count, transaminases, total IgE and specific IgE).

Safety analyses will be done on the treated population.

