## 3.2. THE HYPOTHESES OF THE STUDY AND RESULTS EXPECTED

- The primary hypothesis of the study is that a 16-week treatment with dupilumab is more effective than placebo to improve lesions and symptoms severity in moderate to severe hand eczema refractory to highly potent topical corticosteroids.
- The secondary hypotheses are that a 16-week treatment with dupilumab is more effective than placebo to improve patient pruritus and pain, quality of life, sleep loss, physician and patient global assessment of disease severity, work productivity and AD severity (if appropriate). Another secondary hypothesis is that 16 weeks treatment with dupilumab is a safe option compared to placebo.

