#### 4.2. SECONDARY OBJECTIVES

The secondary objectives are:

- To demonstrate that dupilumab is more effective than placebo to improve pruritus induced by CHE at week 16 as compared to baseline.
- To demonstrate that dupilumab is more effective than placebo to improve pain induced by CHE at week16 as compared to baseline.
- To demonstrate that dupilumab is more effective than placebo to improve quality of life at week 16 as compared to baseline.
- To demonstrate that dupilumab is more effective than placebo to improve sleep loss induced by CHE at week 16 as compared to baseline.
- To demonstrate that dupilumab is more effective than placebo to induce clearance or almost clearance of CHE at week 16 as defined by the investigator and by the patient.
- To demonstrate that dupilumab is more effective than placebo to improve work productivity at week 16 as compared to baseline.
- To evaluate the efficacy of dupilumab on other parts of the body as compared to placebo, in the expected 50% of patients who have eczema not limited to the hand.
- To evaluate the safety of dupilumab as compared to placebo throughout the course of the study.
- To evaluate the evolution of laboratory parameters of patients receiving dupilumab compared to those receiving placebo.

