#### **Adverse events of special interest**

Conjunctivitis will be considered as adverse events of special interest (AESIs) in this trial and must be reported as serious adverse events even if there is no seriousness criteria.

It will require additional details to be recorded in the eCRF. Sponsor may request that the investigator forward complementary information, as appropriate.

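### The safety objective compares dupilumab with placebo, but the safety analysis names only per-arm intervals and gives conjunctivitis, the sole AESI, no overall rate (minor reporting point)

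*Protocol*

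**What the plan says.** The aim is comparative in two places. Protocol 4.2 lists as a secondary objective "To evaluate the safety of dupilumab as compared to placebo throughout the course of the study". Section 3.2 adds: "Another secondary hypothesis is that 16 weeks treatment with dupilumab is a safe option compared to placebo".

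The safety analysis in 13.4 presents treatment-emergent events by MedDRA System Organ Class and Preferred Term. The percentages "will be presented by group with exact 95% Confidence Interval (CI) from study start to study end (Week-20 visit". The same table is repeated for severe and for treatment-related events. Overall percentages are planned for at least one AE and at least one SAE, and one named event gets its own: "The overall percentage of patients reporting injection site reactions will also be presented by group with exact 95% CI". On comparison, the text says: "No statistical test will be performed to compare incidences between groups due to the lack of power and issues with multiplicity testing". It names no risk difference, risk ratio or interval for a difference, and it prohibits none.

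Section 12.3 states: "Conjunctivitis will be considered as adverse events of special interest (AESIs) in this trial and must be reported as serious adverse events", and this applies even when no seriousness criterion is met. On data capture it says: "It will require additional details to be recorded in the eCRF". The follow-up table in 11.2 collects this AESI at six visits (V1, V3, V5, V7, V9 and V10). The safety analysis mentions neither conjunctivitis nor AESIs.

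**The concern.** The question is about a difference between arms, but the only measure of uncertainty offered describes each arm separately. A reader who wants to know how large an excess the data support, or rule out, has two intervals to set beside each other. Checking two 95% intervals for overlap is much stricter than asking whether the interval for the difference excludes zero.

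The reasons given for not testing, low power and multiplicity, argue against p-values. They do not argue against estimating a difference for a few events named in advance. Section 13.4 itself estimates and tests secondary efficacy endpoints between arms without adjusting for multiplicity.

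The one event singled out for special collection also has no summary row of its own. If conjunctivitis is coded to several preferred terms, its total has to be rebuilt from the table or found elsewhere.

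A related counting problem is that non-serious conjunctivitis travels by the SAE reporting route. The percentage with at least one SAE could therefore mix AESIs with events that are truly serious.

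**Working it through.** **Inputs.** The protocol states no figure for the safety analysis and no conjunctivitis rate.
- Patients per arm: section 13.1 plans 84 evaluable patients and 10% non-evaluable. 84 / 0.90 = 93.3, rounded up to 94, which reproduces the stated total. At 1:1 allocation that is 47 per arm. I assume all are treated, because the safety population is the treated population.
- Event counts and true rates: assumptions, varied below.

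**Methods.** Per arm: exact (Clopper-Pearson) 95% CI, taken as the planned exact method. Difference d = p1 − p2: Newcombe interval built from the Wilson limits (l, u) of each arm,
- lower = d − √[(p1 − l1)² + (u2 − p2)²]
- upper = d + √[(u1 − p1)² + (p2 − l2)²]

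**Example, 8/47 v 1/47.**
- p1 = 17.0%, exact CI 7.6 to 30.8%. p2 = 2.1%, exact CI 0.1 to 11.3%. Since 7.6 < 11.3, they overlap.
- Wilson limits: 8.9 to 30.1% and 0.4 to 11.1%. d = 14.9 points.
- Lower = 14.9 − √[(17.0 − 8.9)² + (11.1 − 2.1)²] = 14.9 − 12.1 = 2.8.
- Upper = 14.9 + √[(30.1 − 17.0)² + (2.1 − 0.4)²] = 14.9 + 13.2 = 28.1.

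So the interval for the difference excludes 0 although the per-arm intervals overlap.

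**How often this happens.** Exact enumeration of all binomial outcomes at 47 per arm:

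| Assumed true rates | Difference CI above 0 | Per-arm CIs separate | Difference CI above 0 but per-arm CIs overlap |
|---|---|---|---|
| 10% v 5% | 10% | 1% | 9% |
| 10% v 2% | 28% | 4% | 24% |
| 15% v 5% | 31% | 6% | 25% |
| 15% v 2% | 60% | 19% | 40% |
| 20% v 5% | 58% | 19% | 39% |
| 20% v 3% | 75% | 33% | 41% |
| 25% v 5% | 79% | 39% | 41% |
| 30% v 5% | 92% | 61% | 31% |

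The last column runs from about 9% to 41%. It is largest for excesses of roughly 13 to 20 points, and small for small excesses because neither method then detects much.

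**Effect of splitting the AESI over preferred terms.** Take 10/47 v 2/47 pooled: d = 17.0 points (3.4 to 31.0). If these patients fall, by assumption, into three terms as 4 v 1, 3 v 1 and 3 v 0, the differences are 6.4 (−4.0 to 17.9), 4.3 (−5.7 to 15.2) and 6.4 (−2.3 to 17.2). No single term excludes 0.

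**The case against.** The strongest reply is that nothing in the protocol is wrong here. Declining to test adverse events is a common choice, openly stated and reasoned. The study describes itself as not a confirmatory phase III trial, and the safety objective says evaluate, not demonstrate. Percentages by arm in a blinded randomised trial are already a descriptive comparison, and anyone can compute the difference from the published counts. A grouped AESI row and a risk difference are also details that a SAP may add: the general approach in 13.4 leaves the variables to be described to that document, and the safety text excludes tests, not estimates.

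Much of this stands. A reader might infer that a real excess will be reported as no difference. The documents do not support that. They contain no rule that overlapping intervals mean equal safety, and in the example 17.0% and 2.1% would stand side by side. A reader might also infer that conjunctivitis will be visible only as scattered terms, but System Organ Class rows are planned too and the eCRF captures the AESI directly. Nor can the protocol alone show that the SAP lacks these summaries.

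What remains is that the safety text does fix a format, interval type and time span without deferring to the SAP, and that format fits a comparative objective less well than an equally cheap one. It also gives an overall row to injection site reactions but not to the only AESI.

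**Conclusion.** The point holds as a minor reporting improvement. The objective is comparative, the specified output carries no between-arm estimate, and the sole AESI has no overall rate. At an assumed 47 treated per arm, the per-arm intervals overlap while the difference interval excludes 0 in about 9% to 41% of trials over the assumed rates shown. All these rates are assumptions, and the harm arises only for a reader who judges by overlap.

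It would go too far to say that the planned output cannot answer the safety question, or that it supports a false claim of safety. The per-arm percentages would still show an excess. The primary analysis, the sample size and data collection are unaffected.

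**What to change.** In the safety analysis of 13.4, or in the SAP before unblinding, keep the per-arm percentages, the exact intervals and the decision not to test. Then:

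1. Add one overall row, by arm, for patients with any conjunctivitis AESI, taken from the eCRF AESI record so that the grouping of terms is settled before the data are seen.
2. For four outcomes (any conjunctivitis AESI, any injection site reaction, at least one AE, at least one SAE), report the risk difference dupilumab minus placebo with a 95% CI by the Newcombe or Miettinen-Nurminen method. Label it descriptive, with no p-value.
3. State that the SAE row counts only events meeting a seriousness criterion in section 12.1, so that non-serious conjunctivitis reported by the SAE route is counted in the AESI row and not as an SAE.

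The cost is a few sentences, one added row and four difference estimates. The downside is four unadjusted intervals that could be over-read, and that resolve small excesses poorly: at 10% v 5% the difference interval excludes 0 in only about 10% of trials. The change improves reporting but does not cure low power.

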# 9.2. PROHIBITED ASSOCIATED TREATMENTS/PROCEDURES

Some treatments/procedures are prohibited during the study as either they may influence disease outcome or may pose a safety risk for patients.

Treatment with the following concomitant medications is prohibited during the study

- Treatment with immunomodulating biologics
- Treatment with an investigational drug (other than dupilumab)
- Treatment with topical corticosteroids or topical calcineurin inhibitors; such agents should not be administered during the study.
- Treatment with systemic corticosteroids or non-steroidal systemic immunosuppressive drugs (e.g., cyclosporine, methotrexate, mycophenolate-mofetil, azathioprine, etc.), except if critically medically needed to treat concurrent medical conditions (e.g., asthma).

Study drug will be temporary discontinued (5 half-life before and after vaccination) if a treatment with live (attenuated) vaccine is used through week 16

In addition, major surgery procedure and phototherapy (medical device or tanning) are prohibited during the 16-week treatment period.

**Rescue therapy:** if a patient presents with a severe flare of CHE during the course of the study which cannot be managed with emollients and requires intervention, a unique rescue 2-week course of highly potent corticosteroid (betamethasone dipropionate cream) will be administered. The amount of drug used will be recorded. Study treatment will be unchanged.

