# 12. MANAGEMENT OF ADVERSE EVENTS AND NEW FACTS

# 12.1. DEFINITIONS

#### **Adverse Event** (Article R1123-46 of the Public Health Code)

Any harmful manifestation occurring in a participant in a research study that involves the human person, whether or not the event is related to the research or product to which the research relates.

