#### 12.2. DESCRIPTION OF EXPECTED SERIOUS ADVERSE EVENTS

The serious adverse events expected in the context of this protocol are listed here:

- related to the study treatment (dupilumab): rare hypersensitivity reaction, eyes disorders (severe conjunctivitis or keratitis for example), injection site reaction, herpes infection, hypereosinophilia.
   Other expected adverse events related to dupilumab are described in reference document (IB v.12 (4-Apr-2018)).
- related to the study procedures (blood tests, questionnaires) : none related to evolution of the disease: relapse, flair of hands eczema
  - related to skin biopsy (performed in optional sub-study): skin biopsy may lead to pain, edema, located bleeding, cutaneous infection or healing issue (healing delay, persisting scar...).

Any serious adverse reaction reported in this study will be considered as "unexpected" (SUSAR) if it is not listed in section 10.2 of the protocol or in IB v.12 (4-Apr-2018) of dupilumab.

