#### 12.3. ACTION TO BE TAKEN IN THE CASE OF AN ADVERSE EVENT OR NEW FACT

#### Adverse events collection:

Participating investigators will assess the occurrence of AEs and SAEs at all participant evaluation time points during the study.

All AEs and SAEs whether reported by the participant, discovered during questioning, directly observed, or detected by physical examination, laboratory test or other means, will be recorded in the participant's medical record and on the appropriate study-specific case report forms. All AEs must be recorded in the participant's medical record, stating the duration of the event, action taken by the investigator and outcome of the event. The investigator must evaluate the causal relationship between the study drug and the AE.

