#### Exception to collection:

The following circumstances will not be collected:

- admission for social or administrative reasons,
- hospitalisation predefined by the protocol,
- hospitalisation for scheduled medical or surgical treatment prior to the research,

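### The overall AE and SAE percentages count flares of the hand eczema under study with all other events, so the any-AE figure can understate an excess of other AEs on dupilumab; report both figures with and without flares (minor)

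*Protocol*

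**What the plan says.** Section 12.1 takes the legal definition of an adverse event: "Any harmful manifestation occurring in a participant in a research study that involves the human person", whether or not it is related to the product. Section 12.3 records "All AEs and SAEs whether reported by the participant, discovered during questioning, directly observed, or detected by physical examination, laboratory test or other means". Its exceptions to collection cover three kinds of admission only: social or administrative, predefined by the protocol, and "hospitalisation for scheduled medical or surgical treatment prior to the research". Flares of hand eczema are not excepted.

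Section 12.2, which lists the expected serious adverse events, includes those "related to evolution of the disease: relapse, flair of hands eczema". The line break before this entry is garbled in the text. The word none that precedes it reads naturally with the study procedures item.

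Section 9.2 provides for rescue "if a patient presents with a severe flare of CHE during the course of the study which cannot be managed with emollients and requires intervention".

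Section 12.3 also has conjunctivitis, the adverse event of special interest, reported as an SAE even when no seriousness criterion is met.

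The Safety analysis in section 13.4 plans tables by System Organ Class and Preferred Term, and then: "The same table will be provided for adverse events of severe intensity and for adverse events related to study treatment". On the summary figures it says: "The overall percentage of patients reporting at least one adverse event and at least one serious adverse event will also be computed". It also plans a listing of every SAE with its causality assessment and a separate rate of injection site reactions. No between-group test is planned. The safety hypothesis in section 3.2 is comparative: "Another secondary hypothesis is that 16 weeks treatment with dupilumab is a safe option compared to placebo".

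**The concern.** A flare of the disease under treatment is largely a sign of lack of efficacy. When it counts as an adverse event, the percentage of patients with at least one AE combines treatment failure with other harm. The primary hypothesis expects greater improvement on dupilumab, so flares would be expected more often on placebo. The more effective the drug, the more flares raise the placebo figure relative to dupilumab, and the smaller any excess of other events on dupilumab looks.

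The safety hypothesis is a comparison with placebo and no test is planned, so descriptive percentages carry that comparison. A reader who takes the overall AE percentage at face value could conclude that dupilumab adds few events when it adds more. The Preferred Term rows do not allow the figure to be rebuilt: a patient with both a flare and another event appears in both rows, so the percentage with any AE other than a flare cannot be derived from them.

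**Working it through.** **Inputs.** The protocol gives no AE, flare or SAE rate, so there is no stated safety figure to reproduce. The only protocol number used is the size of the trial (section 13.1): 84 / 0.90 = 93.3, rounded up to 94 randomised, or 47 per arm at 1:1. Every event rate below is an assumption.

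**Formula.** If other events and flares are independent, P(at least one AE) = 1 − (1 − p_other)(1 − p_flare).

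**Any AE.** Assume other AEs in 40% on placebo and 55% on dupilumab, a 15-point excess. With flares in 30% and 10%:
- placebo: 1 − 0.60 × 0.70 = 58.0%
- dupilumab: 1 − 0.45 × 0.90 = 59.5%
- visible excess: 1.5 points.

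Over a range of flare rates:

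| Flares, placebo v dupilumab | Any AE, placebo | Any AE, dupilumab | Visible excess (points) |
|---|---|---|---|
| 10% v 5% | 46.0% | 57.3% | 11.3 |
| 20% v 10% | 52.0% | 59.5% | 7.5 |
| 30% v 10% | 58.0% | 59.5% | 1.5 |
| 40% v 10% | 64.0% | 59.5% | −4.5 |
| 40% v 15% | 64.0% | 61.8% | −2.2 |
| 50% v 20% | 70.0% | 64.0% | −6.0 |
| 20% v 20% | 52.0% | 64.0% | 12.0 |
| 10% v 20% | 46.0% | 64.0% | 18.0 |

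With flares at 10% on dupilumab, the sign changes once placebo flares exceed 1 − (0.45 × 0.90) / 0.60 = 32.5%. With equal flare rates most of the excess survives. If flares are commoner on dupilumab (10% v 20%), the excess is overstated.

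**Precision.** In the 30% v 10% case, 58.0% and 59.5% of 47 are about 27 and 28 patients. The exact 95% intervals are 42% to 72% and 44% to 74%, so the arms would look alike.

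**SAE.** Assume 1% v 4% for SAEs other than flares and conjunctivitis, a 3-point excess.
- With serious flares in 5% v 1%: placebo 1 − 0.99 × 0.95 = 5.9%; dupilumab 1 − 0.96 × 0.99 = 5.0%; difference −1.0 point before rounding of the arms.
- If conjunctivitis reported as SAE is also counted, at 2% v 10%: placebo 1 − 0.99 × 0.95 × 0.98 = 7.8%; dupilumab 1 − 0.96 × 0.99 × 0.90 = 14.5%; difference +6.6 points.

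So flares can hide an SAE excess, and the conjunctivitis rule can inflate one.

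**Severe AEs.** The protocol plans the System Organ Class and Preferred Term table for these, not a single overall percentage. A flare shows on its own term row, and only the class row mixes it with other skin events.

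**The case against.** The strongest reply is that this is table content for the SAP. The AE definition is the statutory one, section 13.4 says that more detail on the variables to describe will come in the SAP, and the SAP is to be validated before unblinding. Much separation is also planned already: Preferred Term tables by group, a table of treatment-related events, an individual SAE listing with causality, and a separate injection-site rate. The overall percentages serve no test or decision rule.

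Most of this stands, and it confines the point to two summary figures. It does not remove it. The safety text itself fixes those figures over all events and, unlike the text on secondary endpoints, defers nothing to the SAP. The related-event table depends on causality judgements, and no overall percentage is planned for it.

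Three stronger readings are tempting, and the protocol supports none of them:
- **That flares will make up a large share of AEs.** No flare rate is given, the rescue provision is a contingency, and the section 12.2 list serves to classify expectedness.
- **That flares are known to fall mainly on placebo.** This is inferred from the efficacy hypothesis. AE counting runs to Week 20, six weeks after the last injection (section 11.1), so flares after treatment ends in dupilumab responders would count too.
- **That the severe-AE and SAE summaries hide toxicity in the same way.** No overall severe-AE percentage is planned, and the conjunctivitis rule pushes the SAE figure up on dupilumab.

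**Conclusion.** The point holds in limited form and is minor. Flares of the study disease fall within AE and SAE reporting, and the protocol plans the two overall percentages only over all events. The any-AE percentage can therefore understate an excess of other AEs on dupilumab, and the SAE percentage is hard to read in either direction.

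The size is unknown. A 15-point excess shows as 1.5 points under one plausible set of assumptions. Across the rates tried, the visible figure runs from −6.0 to 18.0 points. The result rests on assumed event rates, on independence of flares and other events, and on the inference that flares are commoner on placebo. Specific harms remain visible in the term tables and the SAE listing. The documents do not show that a safety signal would be lost altogether.

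**What to change.** In the Safety analysis of section 13.4:
- Keep the all-event percentages as planned.
- Add, by group and with exact 95% intervals, the percentage of patients with at least one AE and with at least one SAE, excluding Preferred Terms for worsening or flare of hand eczema. Fix the term list before unblinding.
- Give the SAE percentage with and without conjunctivitis that meets no seriousness criterion.
- Show flares of hand eczema as their own row, next to the use of rescue therapy.

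Present both sets side by side. The safety comparison should not rest on the flare-excluded set alone, because genuine worsening on dupilumab must stay visible.

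The cost is a few table rows and a blinded classification of terms. No new data are needed, and the conduct of the trial does not change.
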